7.7 Patient Disposition

The number of screened patients will be summarized.

The number of enrolled patients will be summarized, along with the number and percentage of enrolled patients in all of the analysis populations, patients completing the study, patients withdrawing from the study and their primary reason for withdrawal, and the number of deaths, by Part and overall.

Data listings of patient disposition, screening failures, and patient assignment by Part will be created.

7.8 Protocol Deviations

A deviation from the protocol is an unintended and/or unanticipated departure from the procedures and/or processes approved by OncoNano Medicine and the IRB and agreed to by the

principal investigator. Deviations usually have an impact on individual patients or a small group of patients and do not involve inclusion/exclusion or primary endpoint criteria. Deviations which do have a potential impact on the study analyses will be considered “major”.

The number and percentage of patients with at least one major protocol deviation and the categories of the major protocol deviations will be summarized for the Safety population.

All protocol deviations will be provided in a listing.

7.9 Patient Characteristics

Unless otherwise noted, all patient characteristics will use the Safety population.

7.9.1 Baseline and Demographic Characteristics

All baseline characteristics will be summarized by each Part and overall for the Safety population. The following parameters will be summarized:

- Age (years)
- Race
- Ethnicity
- Sex
- Child-bearing Potential (if female)
- Height (cm)
- Weight (kg)
- BMI (kg/m²)
- Karnofsky Performance Status

No hypothesis testing is planned for baseline characteristics, so the analysis will be purely descriptive.

Data listings of baseline characteristics and demographics including Karnofsky Status will be created.

7.9.2 Medical History

Medical history will be summarized for all non-cancer related medical events, previous cancers, and previous anti-cancer therapies. Medical conditions will be coded using Medical Dictionary of Regulatory Activities (MedDRA) 23.0 dictionary or higher and summarized by System Organ Class (SOC) and preferred term (PT) in the Safety population. A listing for the variables above will also be generated.

A summary and listing of previous alcohol, drug, and tobacco use will be provided.

7.9.3 Prior and Concomitant Medications and Procedures/Treatments

Prior and concomitant medication (as well as concomitant procedures/treatments) will be summarized by Part and overall in the Safety population. Medications will be coded with the World Health Organization (WHO) Drug Dictionary (B3 2021-09-01 DDE). Concomitant medications will be summarized by Anatomical Therapeutic Chemical (ATC) Classification System level 2 and 4 codes (ATC2 and ATC4). Procedures/treatments will be coded using MedDRA 23.0 or higher and summarized by SOC and PT. A medication, procedure, or treatment will be considered to be concomitant if its end date is after the date of study drug administration. Medications with a missing end date will also be considered concomitant. A medication with an end date prior to the date of study drug administration will be considered prior medications.

Listings for prior and concomitant medications / procedures will be provided.

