#### 4.3 Study Drug Safety

The most common and anticipated adverse events related to pgsitacianine include infusion related reactions. These reactions occur in about 1 in 3 patients and tend to be mild or moderate in severity. In general, these reactions initiate within 5 minutes of infusion start and resolve within minutes after onset.

Over the doses evaluated in the Phase 1 ON-1001 study (0.1-1.2 mg/kg), pgsitacianine was well tolerated in patients with solid tumors (HNSCC, BC, CRC, or EC) and showed no dose-limiting toxicity (DLT) (hence the maximum tolerated dose was not reached during the study) or study-drug-related serious adverse events (SAEs). Since no pgsitacianine-related SAEs were reported in Phase 1a, the highest dose from Phase 1a [REDACTED] was selected for further evaluation of safety, PK, and imaging feasibility of pgsitacianine in Phase 1b in 15 additional patients across 4 tumor types (BC, HNSCC, CRC, EC) at administration [REDACTED] before surgery (and imaging).

In Phase 1a and 1b, all 30 patients (100%) experienced treatment-emergent adverse events (TEAEs). The most common TEAEs (ie, reported  $\geq 4$  patients overall) were procedural pain (21/30 patients, 70%), nausea (6/30 patients, 20%), wound complication (4/30 patients, 13%), and constipation (4/30 patients, 13%). The TEAEs of procedural pain and wound complication could be attributed to the surgical procedures (standard of care). Severe (Grade  $\geq 3$ ) TEAEs, none related to study drug, occurred in 6 (20%) patients. Overall, 3 patients experienced 4 TEAEs (dizziness, headache, pain in jaw, and flushing) considered possibly related to the study drug. All TEAEs considered related to study drug were mild (Grade 1) and experienced by patients in the [REDACTED] dose cohort. These TEAEs were consistent with typical complications known to occur following surgery, of which the Investigator could not completely rule out the possible contribution of pgsitacianine.

Transient increases in alanine aminotransferase (ALT) (up to 7 $\times$  upper limit of normal [ULN]), aspartate aminotransferase (AST) (up to 10 $\times$ ULN), and/or alkaline phosphatase (up to 3 $\times$ ULN) levels were reported in 4 patients at  $\geq 1$  time point after dosing; none of these abnormalities were considered to be related to the study drug; These elevations were judged by the Investigator to be complications due to the length of surgery and the duration of anesthesia.

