**The Sponsor recommends t**

### ***Dosing and postdose procedures***

Procedures during and after dosing of pegasitacianine are summarized below:

- Dosing of pegasitacianine will be administered
  - , length of infusion and overall volume will depend on the assigned dose and the patient's body weight.
- The following postdose assessments and procedures will occur after infusion of the study drug has been completed:
  - Record the patient's vital signs immediately after the infusion and 30 minutes afterward
  - Discuss any new or unexpected changes in how the patient is feeling
  - Record any AEs
  - Record all medications they are taking, including prescription, over-the-counter, and herbal medications

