**Footnotes**

- a For female patients, a serum sample or urine dipstick for a pregnancy test will be collected at screening and on Day 0 and Day 21.
- b Body mass index will be calculated at Screening only.
- c Vital sign measurements will include systolic and diastolic blood pressure, pulse, respiratory rate, and temperature (in degrees Celsius). Blood pressure and pulse will be measured after a resting period of at least 5 minutes in the supine position.
- d Patient's vital signs are to be recorded immediately after the infusion and 30 minutes afterward
- e The Sponsor recommends the use of prophylactic diphenhydramine prior to study drug administration, in an effort to reduce the prevalence of infusion-related reactions.
- f Patients will be assessed for AEs occurring from the time of dosing through Day 21 ( $\pm 10$  days)
- g Hematology assessments may include hemoglobin, hematocrit, erythrocyte count (red blood cells), differential leukocytes, platelet count, and total leukocytes (white blood cells).
- h Pathologic analysis of surgical specimens will take place from the conclusion of surgery and up to 10 days after

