7.4.1 Dates

Imputation of missing or partial dates is not expected, but if a complete date is required for calculations, the following algorithms will be applied:

- For the start date:
 - If year, month, and day are missing then use the minimum of the patient's first visit date or the consent date.
 - If either only month or month and day are missing then use January 1.

- If only day is missing, impute the first day of the month.
- For the end date:
 - If year, month, and day are missing then use the patient's last visit date.
 - If either only month or month and day are missing then use December 31.
 - If only day is missing then use the last day of the month.
 - Do not expand the record past the patient's last visit.
 - The original missing or partial date, the imputed complete date, and the indicator variable that indicates which dates were imputed will be retained in the database.

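### SAP 7.9.3 leaves a medication that ends on the dosing date neither prior nor concomitant; start-date imputation for AEs and the TEAE end day also need tidying

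*SAP*

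**What the plan says.** **Medications (SAP 7.9.3).** A medication, procedure or treatment is "considered to be concomitant if its end date is after the date of study drug administration". For medications there are two further rules: "Medications with a missing end date will also be considered concomitant", and "A medication with an end date prior to the date of study drug administration will be considered prior medications". No rule covers an end date equal to the dosing date.

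The protocol makes that date a likely one. In Appendix 1, footnote e, "The Sponsor recommends the use of prophylactic diphenhydramine prior to study drug administration". On infusion reactions, Protocol 4.3 says "These reactions occur in about 1 in 3 patients and tend to be mild or moderate in severity" and "In general, these reactions initiate within 5 minutes of infusion start and resolve within minutes after onset". After the infusion, site staff are to "Record all medications they are taking, including prescription, over-the-counter, and herbal medications" (Protocol 6.2). Medications taken since Screening are recorded before dosing (Protocol 6.2), and concomitant medications go into the eCRF (Protocol 4.1).

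**Dates (SAP 7.4.1).** "Imputation of missing or partial dates is not expected, but if a complete date is required for calculations", fixed rules apply. A start date with only the day missing becomes the first of the month. With the month, or month and day, missing it becomes January 1. With everything missing it becomes the earlier of first visit and consent. A limit at the last visit appears among the end-date rules; start dates have no matching limit at dosing. The original date and an imputation indicator are kept.

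**TEAE window.** SAP 7.11.1 counts events from dosing through Day 21. Footnote f of the schedule, in both documents, has AEs assessed through the visit at Day 21 ±10. Protocol 8 has monitoring run to Day 28. The TEAE definition in Protocol 8.1 has no upper limit. SAP section 8 declares no deviations from the protocol.

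**The concern.** The dosing date is the day on which short medication courses tied to the study drug are most likely to start and finish. A rule with a gap there can remove from both summaries the two kinds of medication a reader would want when interpreting infusion reactions: the premedication and the treatment given for a reaction.

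The other two points bear on TEAE tables, which support the secondary safety objective. AEs are collected only after dosing, so a new-onset AE cannot truly start earlier; an imputed start before dosing would be false, and a flag built on it would drop the event. A TEAE window that ends before AE collection does leaves collected events out of those tables, and the SAP does not list this as a departure from the protocol definition.

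**Working it through.** **(a) Classification by end date.** No figure in the plan needs reproducing. Applying SAP 7.9.3 as written to a medication:

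| End date relative to dosing date | As written | With on or after |
|---|---|---|
| 1 or 2 days before | prior | prior |
| same date | neither | concomitant |
| 1 or 2 days after | concomitant | concomitant |
| missing | concomitant | concomitant |

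Only the middle row changes. A procedure or treatment ending on the dosing date is likewise not concomitant as written; SAP 7.9.3 defines no prior class for these.

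Patients who could be affected, out of the planned 40:
- Premedication: 0 to 40. The documents give neither its uptake nor its end date.
- Reaction treatment: at 1 in 3 (Protocol 4.3), 40 / 3 = 13.3 reactions are expected. At the healthy-volunteer rate of 5 of 17 (29.4%), 40 × 5/17 = 11.8. The range is therefore 0 to about 13, reaching the top only if every reaction is treated and every treatment ends that day. In the healthy-volunteer study the reactions resolved on their own, which points to the low end.

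**(b) Imputed start against dosing date.** Assumptions that are not in the documents: dosing dates uniform over a 365-day year, onset uniform over the stated days. The AE is taken to be new-onset after dosing. It is counted as misplaced if its imputed start falls before dosing.

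Only the day missing. The imputed start is before dosing when onset is in the same calendar month as dosing and dosing was not on the first.
- Onset Day 0: (365 − 12) / 365 = 353/365 = 96.7%.
- Days 0 to 7: 365 × 8 = 2920 combinations, 2488 misplaced, 85.2%.
- Days 0 to 21: 365 × 22 = 8030 combinations, 4994 misplaced, 62.2%.
- Days 0 to 31: 365 × 32 = 11680 combinations, 5373 misplaced, 46.0%.

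Month and day missing (start set to January 1): 364/365 = 99.7% for Day 0, 7777/8030 = 96.8% for Days 0 to 21, 11152/11680 = 95.5% for Days 0 to 31.

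Whole date missing: always before dosing, because consent and the first visit fall in Days −30 to −1.

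With a floor at the dosing date, the share is 0 in every case. All these percentages are conditional on an incomplete date. The documents give no rate of incomplete dates, so no event count follows.

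**(c) Windows side by side.**

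| Source | End of window |
|---|---|
| SAP 7.11.1, TEAE | Day 21 |
| Footnote f, AE assessment | Day 21 ±10, so Days 11 to 31 |
| Protocol 8, AE monitoring | Day 28 |
| Protocol 8.1, TEAE | none |

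With a fixed Day 21, the collected days outside the TEAE window number 31 − 21 = 10 at most under footnote f, and 28 − 21 = 7 under Protocol 8. For a patient seen on Day 21 or earlier the number under footnote f is 0; for one seen on Day 31 it is 10 of 32 collected days (Days 0 to 31). Of the 21 permitted visit days, 17 fall before Day 28 and 3 after it, so Protocol 8 and footnote f rarely give the same end. These are days, not events; no rate of late AEs is given.

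**The case against.** On (a), the effect is on descriptive medication tables, and a programmer would probably notice. That limits the weight, but SAP 7.1 relies on independent programming and a check for consistency with the plan, and the plan has no rule here for two programmers to agree on. A reader might infer that premedication will be missing for all 40 patients. The documents do not support that: it is a recommendation, uptake is unknown, and neither the calendar date nor the end date is stated.

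On (b), the objection is strong. The rule is generic, applies only where a complete date is required, and is not expected to be used. Since AEs are collected only after dosing, a new-onset AE could be flagged by collection with no imputed date; the SAP does not say so, but nothing forbids it. The retained original date makes an error visible and reversible. The highest percentage is also the least realistic, because it needs a Day 0 event whose day nobody recorded. A reader might infer from the percentages that many TEAEs would be lost. They describe only events with incomplete dates, which may be none.

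On (c), a reader might infer that the SAP's Day 21 is ambiguous between a fixed day and the visit. It is not a persuasive reading: the text plainly describes a fixed day, and the SAP writes the visit with its ±10 window. A uniform window is a legitimate choice, and SAP section 1 lets the SAP overrule the protocol on analysis. Replacing it with each patient's last assessment would trade one drawback for another, since the window would then end anywhere from Day 11 to Day 31. What stands is that the limit differs from Protocol 8.1, that section 1 promises to document deviations, and that section 8 lists none.

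**Conclusion.** Part (a) holds exactly and needs no assumption: an end date on the dosing date has no class under SAP 7.9.3. How many patients this touches cannot be known from the documents. Part (b) holds conditionally: it matters only if an AE start date is incomplete and the imputed date is used for the TEAE flag. Then misplacement is usual for early onsets, but few events, if any, are expected. Part (c) is a matter of reconciliation: under the fixed Day 21, AEs collected on Days 22 to 31 stay out of the TEAE tables, and this is not declared.

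The whole is minor. A reader might infer that the trial's safety findings or its main result are at risk. They are not: the primary endpoint, the overall AE count, the AE listing, the SAE summaries and the infusion-reaction summaries do not depend on these rules. The exposure is confined to the medication summaries and, conditionally, the TEAE tables.

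**What to change.** - **SAP 7.9.3:** define concomitant as an end date on or after the dosing date. Cost: a medication stopped on Day 0 before the infusion will count as concomitant.
- **SAP 7.4.1:** for AEs, where the known date parts allow onset on or after dosing, do not impute a start earlier than the dosing date.
- **TEAE window:** reconcile SAP 7.11.1, footnote f, Protocol 8 and Protocol 8.1. If the Day 21 limit is kept, list it in SAP section 8 as a deviation from the protocol.

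This takes a sentence in each of SAP 7.9.3 and 7.4.1, an entry in SAP section 8 if the limit stays, and one protocol clarification of when AE collection ends. No new data are needed. Medication and TEAE counts may shift slightly. SAP 7.1 allows such updates before database lock.

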7.9.4 Administration and Exposure of Study Drug

Administration of study drug (planned dose level, total dose administered, total volume administered, infusion flow rate, infusion duration, subjects with infusion reactions, and subjects with dose interruptions) will be summarized using descriptive statistics. Infusion flow rate will be calculated as total volume administered ÷ infusion duration. A listing will also be generated.

7.9.5 Surgery Details and Specimen Collection

Surgery details including the following will be summarized on a patient level using descriptive statistics in the Safety population:

- Duration of surgery
- Location of tumor

- Method of tumor localization, including number of subjects with primary tumor(s) identified using NIR imaging
- Number of SOC specimens collected
- Number of additional lung nodules/areas found as a result of NIR imaging following SOC procedures and confirmed to be cancer
- Number of SOC specimens collected, found to be negative for tumor, and did not fluoresce during *ex situ* imaging
- Number of areas with fluorescence removed on:
 - Lung resection margins
 - Thoracic cavity
 - Lymph nodes
 - Total (any area)
- Number of areas with fluorescence on lung resection margins
- Subjects with fluorescence observed anywhere in thoracic cavity
- Number of lymph nodes collected as SOC surgery
- Time spent imaging
- Camera system used

A listing will also be generated.

7.10 Efficacy Endpoint Analyses

Imaging will be assessed on the Efficacy population.

7.10.1 Primary Analyses

7.10.1.1 Analysis of Clinically Significant Events

The number and proportion of subjects with CSEs will be summarized by Part and overall. CSE responders will be summarized, as well as subjects with each type of CSE. These summaries will include 95% 2-sided confidence intervals for the proportion of CSEs calculated via Clopper-Pearson method.

A listing of all CSEs by patient will be provided.

7.10.2 Secondary Analyses

7.10.2.1 Analysis of Diagnostic Imaging

The positive predictive value, negative predictive value, sensitivity, and specificity (specimen level) will be calculated and summarized for each Part and overall. The summary will include the true/false negative/positive rate and number of specimens. Two-sided 95% confidence intervals will be calculated for each rate via Clopper-Pearson method.

A listing by subject and specimen showing the specimen type (primary tumor/ additional SOC specimen, lung resection margin, thoracic cavity, lymph node), attainment by SOC or fluorescence (if primary/ additional SOC/ lymph), pathology result, fluorescence *in situ* and *ex situ*, and fluorescence measures (MFI and TBR) will be provided.

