2. STUDY OBJECTIVES

2.1 Objectives and Endpoints

The primary objective of this study is to investigate whether pegasitacianine can detect clinically significant events (CSEs) at the patient level, which include:

1. The detection of disease that cannot be detected using standard procedures during the surgical resection of lung malignancies
2. The detection of synchronous lesions
3. The detection of positive surgical margins following primary tumor resection
4. Tumor-negative standard of care (SOC) biopsies

Table 1. Objectives and Endpoints

Objectives	Endpoints
Primary Objective	Primary Endpoint
The primary objective of this study is to investigate whether pegasitacianine can detect clinically significant events (CSEs) at the patient level.	Rate of CSEs, which include: 
1. The detection of disease that cannot be detected using standard procedures during the surgical resection of lung malignancies2. The detection of synchronous lesions3. The detection of positive surgical margins following primary tumor resection4. Tumor-negative standard of care (SOC) biopsies

Secondary Objectives	Secondary Endpoints
Determine sensitivity, specificity, negative predictive values (NPPV), and positive predictive values (PPV) of the imaging agent at the level of the individual specimens, including lymph nodes.	Sensitivity, specificity, negative predictive values (NPV), and positive predictive values (PPV) at the specimen-level.
Evaluate safety and toxicity of pegsitacianine.	Incidence of TEAEs and SAEs, abnormalities in lab values, vital signs, or ECG results.
Exploratory Objectives	Exploratory Endpoints
Assess the how the SBR affects the diagnostic accuracy of pegsitacianine in detection of metastatic disease vs. normal tissue.	ROC analysis across various tumor-to-background ratio fluorescence thresholds.
Effect of camera system on diagnostic results.	Diagnostic results across various camera systems.
Assess amount of fluorescence shown in various types of specimens.	Mean fluorescence intensity and Specimen-to-background ratio

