3. STUDY DESCRIPTION

3.1 Study Design

This Phase 2 study will be an interventional, open-label, single arm trial where each patient is his/her own “intrapatient” control. All patients will receive a single █ mg/kg dose of pegsitacianine administered █ prior to standard of care (SOC) surgery. The study will be conducted in two Parts. Part 1 will enroll patients undergoing minimally invasive procedures (i.e., video-assisted thorascopic surgery [VATS] or robotic surgery). Part 2 will be opened at the discretion of the Sponsor and include patients undergoing open thoracotomy for the removal of their disease. [Note: Part 2 was not opened to enrollment.]

Patients will have a biopsy confirmed diagnosis, or a high clinical suspicion of a lung malignancy based on CT and/or PET imaging. A total of up to 40 patients will be enrolled in this trial. The sponsor reserves the right to perform an interim analysis following early enrollment (n ≤ 10 subjects) to determine the feasibility and benefit of pegsitacianine as an adjunct to SOC surgery.

The surgeon will attempt to perform their SOC resection of visible tumors. If the tumor is unable to be located under standard white light conditions, an appropriate near-infrared (NIR) imaging device may be used to aid in the location of the primary tumor. Localization of the primary tumor using NIR imaging in conjunction with pathology confirmed presence of disease will be considered a clinically significant event.

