5.1.2 Diagnostic Imaging Endpoints

Diagnostic performance of pegsitacianine will be assessed by calculating sensitivity, specificity, NPV, and PPV of pegsitacianine in detecting tumor containing tissue. The *ex situ* fluorescence status (any fluorescence vs. no fluorescence) of collected SOC and pegsitacianine guided specimens, as well as lymph nodes, will be compared to histological analyses of the collected specimens. Sensitivity and specificity for detecting tumor-containing tissue versus normal tissue

will be evaluated using tissue specimen fluorescence and the corresponding pathological outcomes.

True/false/negative/positive definitions are as follows:

- False positive is defined as fluorescence was observed on the sample but the sample was not found to have tumor via pathology.
- False negative is defined as no fluorescence was observed on the sample but the sample was found to have tumor via pathology.
- True positive is defined as fluorescence was observed on the sample and the sample was found to have tumor via pathology
- True negative is defined as no fluorescence was observed on the sample and the sample was found not to have tumor via pathology.

Pegsitaricaine sensitivity and PPV will be calculated using the following equations:

$$\text{Sensitivity} = \frac{\text{\# of True Positive Specimens}}{\text{\# of True Positive Specimens} + \text{\# of False Negative Specimens}}$$

$$PPV = \frac{\# \text{ of True Positive Specimens}}{\# \text{ of True Positive Specimens} + \# \text{ of False Positive Specimens}}$$

Pegsiraniline specificity values and NPV will be calculated using the following equations:

$$\text{Specificity} = \frac{\text{\# of True Negative Specimens}}{\text{\# of True Negative Specimens} + \text{\# of False Positive Specimens}}$$

$$NPV = \frac{\# \text{ of True Negative Specimens}}{\# \text{ of True Negative Specimens} + \# \text{ of False Negative Specimens}}$$

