7.10.3.4 Other Exploratory Analyses

Relationships of sensitivity and specificity may be evaluated post-hoc with respect to additional covariates including, but not limited to, tumor size, tumor type, and tumor location.

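### Sensitivity and specificity are planned only for all specimen types pooled, so a fluorescence difference between lung tissue and lymph nodes could pass for tumor detection

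*SAP*

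**What the plan says.** The secondary objective in SAP 2.1 is to determine the four accuracy measures "of the imaging agent at the level of the individual specimens, including lymph nodes". SAP 5.1.2 defines what enters the table: the any-versus-none fluorescence status of standard-of-care and "guided specimens, as well as lymph nodes, will be compared to histological analyses of the collected specimens". SAP 7.10.2.1 then gives the only summary: "The positive predictive value, negative predictive value, sensitivity, and specificity (specimen level) will be calculated and summarized for each Part and overall", with Clopper-Pearson intervals. Protocol 9.4 pools in the same way. SAP 3.1 adds "Note: Part 2 was not opened to enrollment", so the by-Part and overall results are the same table.

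Specimen type appears in three other places:

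- SAP 7.10.2.1 plans "A listing by subject and specimen showing the specimen type (primary tumor/ additional SOC specimen, lung resection margin, thoracic cavity, lymph node"). This is a listing, with no estimates.
- SAP 2.1 has an exploratory objective, "Assess amount of fluorescence shown in various types of specimens", but its endpoints are intensity and specimen-to-background ratio. The matching summary in SAP 7.10.3.1 splits by pathology result, not by specimen type.
- SAP 7.9.5 counts, per patient, the fluorescent areas removed from margins, cavity and nodes, and the standard-of-care nodes collected. It does not cross fluorescence with pathology within each type.

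SAP 7.10.3.4 says "Relationships of sensitivity and specificity may be evaluated post-hoc with respect to additional covariates". That is optional and does not name specimen type.

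**The concern.** Specimen type is likely to be related to tumor status. Entry requires a confirmed or highly suspected lung malignancy (Protocol 5.1), so primaries should often be malignant. Lymph nodes taken as part of standard surgery may well have a different malignant share. If the two tissues also differ in how often they fluoresce for reasons unrelated to tumor, tissue type acts as a confounder: fluorescence marks the tissue, the tissue predicts the pathology, and the pooled table shows an association that exists in neither tissue.

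The pooled values also depend on the mix of specimens collected and may describe no actual tissue. A reader interested in nodes, which the objective singles out, would have no estimate for them. Protocol 9.1 says the study is meant to inform power calculations for future studies, and those need tissue-specific rates.

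**Working it through.** **Figure in the plan.** There is none to reproduce. The 40 subjects in Protocol 9.1 and SAP 4 rest on historical experience, with no specimen count and no expected sensitivity or specificity.

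**Could another planned analysis separate the tissues?** The ROC analysis (SAP 7.10.3.2) uses all specimens. Its mixed model clusters by subject, but one subject can contribute both a primary and nodes, so clustering does not adjust for tissue. SAP 7.10.3.3 splits by camera. Neither gives accuracy by specimen type.

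**Inputs, all assumed.** 40 primaries (one per subject), of which 85% malignant = 34 tumor, 6 not. Nodes: 80, 120 or 200, of which 5%, 10% or 20% malignant. Fluorescence probability gP in primaries and gN in nodes, the same for tumor and non-tumor within each tissue, so true discrimination is zero.

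**Formula.** Let a be the share of tumor specimens that are primaries and b the share of non-tumor specimens that are primaries.

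- Pooled sensitivity = a·gP + (1 − a)·gN
- Pooled specificity = 1 − [b·gP + (1 − b)·gN]
- Sensitivity + specificity − 1 = (gP − gN)(a − b)

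The last line is zero if the fluorescence rates are equal, or if a = b, which is the case when the malignant shares are equal.

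**Example.** 80 nodes, 4 malignant; gP = 80%, gN = 20%.

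| | TP | FN | FP | TN | Sensitivity | Specificity | Odds ratio |
|---|---|---|---|---|---|---|---|
| Primaries | 27.2 | 6.8 | 4.8 | 1.2 | 80% | 20% | 1.0 |
| Nodes | 0.8 | 3.2 | 15.2 | 60.8 | 20% | 80% | 1.0 |
| Pooled | 28 | 10 | 20 | 62 | 28/38 = 73.7% | 62/82 = 75.6% | (28×62)/(10×20) = 8.7 |

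Check: (0.80 − 0.20)(34/38 − 6/82) = 0.60 × 0.822 = 0.49, which equals 0.737 + 0.756 − 1.

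**Range.** Nine node scenarios at each of three pairs of fluorescence rates:

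| gP / gN | Pooled sensitivity | Pooled specificity | Both at least 70% |
|---|---|---|---|
| 90% / 10% | 46.8–81.6% | 83.1–87.6% | 4 of 9 |
| 80% / 20% | 47.6–73.7% | 74.9–78.2% | 2 of 9 |
| 70% / 30% | 48.4–65.8% | 66.6–68.8% | 0 of 9 |

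In total both reach 70% in 6 of 27. The example above has the highest sensitivity of its row. At 70/30 the level cannot be reached, because pooled sensitivity is a weighted average of 70% and 30%. With gP = gN = 50%, sensitivity + specificity − 1 is 0.

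**Where the agent does work.** Assume sensitivity 90% in primaries and 40% in nodes, specificity 40% and 90%, and 120 nodes with 12 malignant. Pooled sensitivity = (34×0.9 + 12×0.4)/46 = 35.4/46 = 77%. Pooled specificity = (6×0.4 + 108×0.9)/114 = 99.6/114 = 87%. The pooled pair describes neither tissue.

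**The case against.** **The inputs are assumed.** The documents give no malignant share for primaries or nodes, no node count and no fluorescence rate by tissue. This stands. Only the high suspicion of malignancy at entry is documented. Nothing shows that the tissues fluoresce at different rates, and specimens are imaged against normal tissue, which offers some reference. However, the documents do not say that the reference tissue must match the specimen type, and the status used is any fluorescence versus none, not a ratio.

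**Some information by type exists.** It does: the listing, and the counts in SAP 7.9.5. So one cannot say that specimen type is never tabulated. Neither yields sensitivity or specificity by type. The separate tables document is not available here, but the SAP text does not call for such a table.

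**Pooled sensitivity as a primary-tumor figure.** A reader might infer that it is essentially that. This does not hold throughout: with 200 nodes at 20% malignant there are 40 malignant nodes against 34 malignant primaries, and pooled sensitivity at 80/20 falls to 47.6%, which exposes weak nodal performance rather than hiding it.

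**The 70% level.** A reader might infer that a decision hangs on it. Protocol 3.1 ties it to opening Part 2, which did not open, so it serves here only as a yardstick.

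**Small cells.** Malignant nodes and benign primaries may be few. That is true, and it limits what a split can show. Pooling hides the scarcity but does not cure it.

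**Conclusion.** The concern holds as a gap in the planned reporting. All specimen types go into one table and no accuracy by type is planned, while the objective names lymph nodes. The pooled figures can show apparent accuracy with no discrimination in either tissue, provided that both the malignant share and the fluorescence rate differ between tissues. Under the assumed ranges, sensitivity + specificity − 1 runs from 0.17 (70/30, 200 nodes, 20% malignant: 0.484 + 0.686 − 1) to 0.66 (90/10, 80 nodes, 5% malignant: 0.816 + 0.841 − 1), when the true value is zero.

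It would go too far to conclude that the agent fails to discriminate, that the pooled results will be an artifact, or that clearing 70% on both measures is the typical outcome. The documents support none of these. The pooling is certain; its size in this trial is unknown. What is affected is the reading of a descriptive secondary endpoint in a study not powered for testing, and the rates carried into later designs.

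**What to change.** In SAP 7.10.2.1, add a table of 2x2 counts, sensitivity, specificity, PPV and NPV with 95% intervals, separately for (a) primary and additional standard-of-care lung specimens and (b) lymph nodes.

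For lung resection margins and thoracic-cavity specimens taken after standard resection, report counts and PPV only. SAP 5.1.1 treats all of these as collected because of fluorescence, so non-fluorescent tissue there is not sampled on the same terms, and selection distorts sensitivity, specificity and NPV. Nodes taken because they fluoresced carry the same selection. The listing already records how each node was obtained, so a footnote can give their number.

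Keep the pooled row beside these and draw no accuracy conclusion from it alone.

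The cost is one more table from a field already recorded. Some intervals will be very wide: with 4 malignant nodes, as in the example, an observed 2 of 4 has an exact 95% interval of 7% to 93%, and lung-specimen specificity would rest on 6 benign primaries.
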